9.4 STATISTICAL ANALYSES

9.4.1 General Approach

For comparisons of before and after device intervention in the same participant and correlation calculations, statistical significance will be determined by corresponding parametric (e.g., paired t-test and Pearson correlation) or non-parametric (Wilcoxon Rank sum test and Spearman correlation) methods. A p value < 0.05 will be considered significant and between 0.05 and 0.10 will be considered a trend. Multiple comparisons will be corrected by appropriate post-hoc analysis.

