9.4.3 Analysis of the Secondary Endpoint(s)

Function Test – Efficacy Scores

Data analysis. Participants' scores will be the sum of items 1 to 7 combining levels a & b and will range from 0 to 14, and the mean duration to complete each task. Analysis will consist of change in scores and mean duration to complete each task from baseline to 1 week and 1 month). No formal statistical tests will be conducted. Interpretation of results will be rule-based.

Rules for data interpretation. Device use is efficacious if at 1-week or 1-month compared to baseline:

- 25% or more of total number of participants increased score by at least 30%
- 25% or more of total number of participants decreased time by at least 30%

Below are some simulations of the power of a paired-sample test for change from baseline, using a sample size of 10 participants. This provides a sense of the possible characteristics of the data and for justifying the sample size.

Simulations for tasks-completed scores

Each simulation study used 1000 replications with $N = 10$. For each replication, baseline and post-baseline sets of scores were randomly generated. Means, standard deviations, and paired-samples t-tests of difference scores (Post-baseline – Baseline)

were computed. Power was computed by the percent of replications (out of 1000) with t-test p-values less than or equal to 0.05. Baselines were generated by randomly selecting, with replication, scores from 0 to 5 with equal probability, 1/6. The baseline range matched the baseline values reported in the adult study. Post-baseline scores included a specified number of baseline cases randomly selected without replacement to improve by 30% (Baseline \times 1.30). Cases with baseline values = 0 were excluded from random selection since percentage change from 0 is undefined.

Simulation 1. Based on the decision rule of 25% of total participants, 3 cases (rounded up since 25% of N= 10 is 2.5) were randomly selected to improve 30% from baseline and the other 7 cases did not improve. *Results: power = proportion of 1000 p-values <= 0.05 = 0.37.*

Simulation 2. 3 cases randomly selected to improve 30% and 7 cases improved by 1 point. *Results: power = proportion of 1000 p-values <= 0.05 = 1.0.*

Simulation 3. 4 cases randomly selected to improve 30% and 6 cases did not improve. *Results: power = proportion of 1000 p-values <= 0.05 = 0.95.*

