Simulation 4. 4 cases randomly selected to improve 30%, 6 cases improved by 1. *Results: power = proportion of 1000 p-values <= 0.05 = 1.0.*

Simulation 5. 2 cases randomly selected to improve 30% and 8 cases did not improve. *Results: power = proportion of 1000 p-values <= 0.05 = 0.00.*

Simulation 6. 2 cases randomly selected to improve 30%, 8 cases improved by 1. *Results: power = proportion of 1000 p-values <= 0.05 = 1.0.*

Simulations with baseline values 1 to 5, # cases improving 30%: 2 to 5; # cases improving by 1: 0 to 3; # cases no improvement: 4 to 8. (For any simulation run, # cases improving 30% + #cases improving by 1 + # cases not improving = 10).

Results: These simulations correct for the problem that percentage improvement is undefined when baseline = 0. When stipulating that percentage improvement is 30% for as few as 2 or 3 cases, power is greater than .99 when only 1 to 3 other randomly selected cases improve by 1 from baseline. Power will be higher if participants' scores improve more than 1 over baseline.

Based on these simulations, a test of efficacy using a paired-samples t-test with N = 10 would be adequately powered provided that post-baseline scores are likely to improve from baseline. Whether or not a sample of 10 is large enough to make conclusions about different characteristics of the sample group is not addressed.

Ability Questionnaire

Data analysis. Proportions of participants with scores 3 or greater in all items from 1-12. No formal statistical tests will be conducted. Interpretation of results will be rule-based.

Rules for data interpretation. Device use is efficacious if there is a 25% increase in the proportion of participants scoring 3 or greater in all items at 1-week or 1-month as compared to baseline.

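### Section 9.4.3 calls an N = 10 paired t-test adequately powered, but its own simulation at the 25% efficacy threshold prints power 0.37, and that figure holds only for an unstated one-sided test

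*Combined protocol and SAP*

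**What the plan says.** For the Function Test score, Section 9.4.3 declares the device efficacious if "25% or more of total number of participants increased score by at least 30" per cent at 1 week or 1 month, compared with baseline. The same section says that the endpoint will be read by rule, with no formal test. It then gives power simulations for a paired test with 10 participants, offered partly to justify the sample size.

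Simulation 1 is tied to the rule: "Based on the decision rule of 25% of total participants, 3 cases (rounded up since 25% of N= 10 is 2.5"). Those three improve by 30% and the other seven do not change. Its result is "power = proportion of 1000 p-values <= 0.05 = 0.37". Simulation 3 (4 improve, 6 do not) prints 0.95. Simulation 5 ("2 cases randomly selected to improve 30% and 8 cases did not improve") prints 0.00. Simulations 2, 4 and 6, in which every remaining participant gains one point, print 1.0. A further set with baselines of 1 to 5 is summarised as giving power above .99 when 2 or 3 cases improve by 30% and 1 to 3 others gain a point.

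The closing sentence, offered as following from these simulations, is that "a paired-samples t-test with N = 10 would be adequately powered provided that post-baseline scores are likely to improve from baseline".

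Power is counted as the share of replications "with t-test p-values less than or equal to 0.05". Neither this section nor Section 9.4.1 says whether the test is one- or two-sided. Section 9.4.1 says only: "A p value < 0.05 will be considered significant and between 0.05 and 0.10 will be considered a trend".

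**The concern.** Simulation 1 is the one scenario set exactly at the effect the plan calls efficacious, and there the test misses the effect in about 63% of replications (1 − 0.37). The proviso does not repair this. In Simulation 1 nobody declines and the mean rises, so scores do improve. If the proviso instead means that more participants improve than the rule requires, the sentence no longer covers the effect that the plan itself treats as success.

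Ten is also the size of the non-CLN3 cohort, and Section 9.4.7 refers sub-group analyses back to Sections 9.4.2 and 9.4.3. Anyone who applied the general paired test of Section 9.4.1 to that cohort, relying on the closing sentence, could take a non-significant result as evidence that the device does not help.

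**Working it through.** **Inputs (Section 9.4.3).** N = 10; baselines equally likely from 0 to 5; zero baselines cannot be chosen as improvers, so each improver's baseline is equally likely to be 1, 2, 3, 4 or 5; an improver gains 0.3 × baseline; paired t-test with 9 degrees of freedom; success is p ≤ 0.05.

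**Formula.** Let S be the sum of the ten differences and Q the sum of their squares. Then

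t = S√(N − 1) / √(NQ − S²).

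So t ≥ c exactly when S²/Q ≥ Nc²/(N − 1 + c²). For N = 10:

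- one-sided 0.05: c = 1.833, so S²/Q must reach 10 × 3.360 / 12.360 = 2.72;
- two-sided 0.05: c = 2.262, so S²/Q must reach 10 × 5.117 / 14.117 = 3.62.

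With k non-zero differences, S²/Q cannot exceed k, and it equals k only when the gains are equal. The largest possible t is therefore √(9k/(10 − k)): 1.50 for k = 2, 1.96 for k = 3, 2.45 for k = 4. Two improvers can never be significant on either test. Three can never be significant two-sided; the smallest attainable two-sided p-value is 0.081.

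**Reproducing the printed powers.** Counting all equally likely improver baselines (5^k of them):

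| Scenario | Printed | One-sided | Two-sided |
|---|---|---|---|
| Sim. 1: 3 improve, 7 unchanged | 0.37 | 47/125 = 0.376 | 0/125 = 0.00 |
| Sim. 3: 4 improve, 6 unchanged | 0.95 | 605/625 = 0.968 | 193/625 = 0.309 |
| Sim. 5: 2 improve, 8 unchanged | 0.00 | 0/25 = 0.00 | 0/25 = 0.00 |
| Sims. 2, 4, 6: all others gain 1 (simulated) | 1.0 | 1.00 | 1.00 |

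The one-sided column agrees with every printed figure to within 0.02. The two-sided column does not: it gives 0.00 for 0.37 and 0.31 for 0.95. That the simulations were one-sided is thus an inference from the figures. A positive t with one-sided p ≤ 0.05 has two-sided p ≤ 0.10. Since three improvers cannot get below 0.081 two-sided, every success counted in Simulation 1 would be only a trend under Section 9.4.1 if its p-values are two-sided.

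**The .99 statement (baselines 1 to 5).**

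| Cases at +30% | Others at +1 | One-sided | Two-sided |
|---|---|---|---|
| 2 | 1 | 14/25 = 0.56 | 0.00 |
| 2 | 2 | 1.00 | 16/25 = 0.64 |
| 2 | 3 | 1.00 | 1.00 |
| 3 | 1 | 1.00 | 52/125 = 0.42 |
| 3 | 2 or 3 | 1.00 | 1.00 |

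One-sided, the statement holds except for 2 + 1. Two-sided, it fails for 2 + 1, 2 + 2 and 3 + 1.

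**Where the high powers come from.** They need more improvers than the rule minimum, or added one-point gains. A one-point gain is itself at least 30% for baselines of 1 to 3 (1/3 = 33%; 1/4 = 25%), so Simulations 2, 4 and 6 lie well beyond the rule's threshold.

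**Planned sample.** At N = 30 the rule needs 0.25 × 30 = 7.5, rounded up to 8 improvers. With 8 improving by 30% and 22 unchanged, power is 1.00 one- or two-sided.

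**The case against.** The strongest reply is that nothing in the trial turns on this test. Section 9.4.3 plans no formal test for the Function Test, so low t-test power cannot change whether the 25%/30% rule is met. Section 4.1 assesses the secondary objective in all 30 participants, where the same model gives power of about 1.00. Both points stand, and they limit the consequence. A reader might infer that the trial is underpowered for its secondary objective, or that the efficacy rule is undermined; the documents support neither.

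It can also be said that the closing sentence is conditional, that the low powers are printed openly, and that the plan says it does not address whether 10 is enough for conclusions about different characteristics of the group. The openness is to the plan's credit. But that caveat is not about power, and the condition is satisfied in the scenario that prints 0.37.

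Two further inferences should be resisted. Simulation 5 does not show a missed efficacious effect, because 2 of 10 is 20%, below the rule. Nor is there support for saying that the sentence would mis-size the follow-on trial: Section 9.2 says the pilot data will inform that calculation, and also that power could not be determined here.

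**Conclusion.** The closing sentence is wrong as written. At the plan's own threshold, N = 10 gives power of about 0.37 under the reading most favourable to it (one-sided) and 0.00 under a two-sided test. With one more improver it is about 0.97 one-sided (printed 0.95) and 0.31 two-sided. The .99 statement is wrong at its lower end even one-sided.

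This is a fault in the N = 10 justification only. It bears on any stand-alone test in a group of 10, not on the decision rule or the full sample.

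The figures rest on the plan's simulation model: gains of exactly 30%, and no change at all in the others. The plan sets no target for adequate power; against an assumed conventional 80%, 0.37 falls short by 43 percentage points.

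**What to change.** Remove the statement that N = 10 is adequately powered. Replacement text could read:

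> With N = 10, power at the efficacy threshold (3 of 10 improving by 30%, others unchanged) is about 0.37 with a one-sided 0.05 test and 0.00 with a two-sided 0.05 test. With 4 of 10 improving it is about 0.97 one-sided and 0.31 two-sided. Higher power requires more improvers than the rule minimum, or one-point gains in one or more other participants. At the planned N = 30 with the rule minimum of 8 improvers, power is about 1.00 under the same model. Any non-significant test in a group of 10 will not be interpreted as absence of efficacy.

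Also state whether the simulations were one- or two-sided, and correct the .99 statement, at least by excluding the case of 2 improvers plus one one-point gain.

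The cost is one paragraph of wording, with no added participants, visits or data. The downside is a less favourable stated power.

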4 STUDY DESIGN

4.1 OVERALL DESIGN

Individuals with CLN3 are anticipated to have vision loss and intellectual disability, but with preserved auditory function. We **hypothesize that an auditory-based assistive technology with a simple operating procedure, such as the OrCam, will be safe and feasible for use in a pediatric population, including those with CLN3, and will enhance their ability to obtain visually based information.** We propose a pilot study of 20 study participants to evaluate the safety, feasibility, and efficacy of using the OrCam in a cohort of the CLN3 pediatric population. Since no information is available on the safety, feasibility and efficacy of the OrCam in the

Abbreviated Title: Pediatric Optic-to-Audio Device Study

Version Date: March 8, 2022

pediatric population, we also propose enrolling 10 pediatric participants with low vision from non-CLN3-related causes. The primary and secondary objectives will be assessed using data from all 30 participants.

In this 2-cohort (CLN3 and non-CLN3), open-label, single-center study, we aim to determine:

- 1) the safety and feasibility
- 2) the potential clinical efficacy

of the use of OrCam in children, including individuals with CLN3.

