8.2.1 Clinical Evaluations

1. **Function Test.** The study participants will be asked to complete tasks relating to device-supported daily activities (**Appendix C**). These include identification of printed words (e.g., books, documents, menus, labels, signs) and identification of faces and colors. At Days 1 (baseline) and 5 (1-week evaluation), the Function Test will be done in its entirety via face-to-face encounters. A sub-group of the Function Test items may be done via the use of remote technologies (e.g., videoconferencing). At the 1-month evaluation, if the study participants are able to come to the NIH the Function Test will be done as on Days 1 and 5. If study participants are not able to come for an in-person visit, the sub-group of the Function Test items will be done remotely.
2. **Ability and Applicability Questionnaires.** Parents/Guardians will complete questionnaires of their child's ability to accomplish the tasks in the Function Test without help, and their ratings of how important it would be for their child to accomplish these

tasks without help. (**Appendices D, E**). The questionnaires may be completed using paper or web-based format.

3. **Neuropsychologic Evaluation.** We will assess adaptive behavior using *The Vineland Adaptive Behavior Scales*, Third Edition, Daily Living Scale, based on parent interview. This may be done by methods that do not require in-person meetings (such as via a phone call) to provide adaptability to the protocol and to maximize ability to collect meaningful longitudinal data.
4. **Quality of Life Questionnaires.** Parents/Guardians will complete age-appropriate PedEyeQ[27], PROMIS[28], and Low Vision QOL[29] questionnaires (**Appendices G - I**). The questionnaires may be completed using paper or web-based format.

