Appendix A. Feasibility Test

Appendix B. Feasibility Questionnaire

Appendix C. Function Test

Appendix D. Ability Questionnaire

Appendix E. Applicability Questionnaire

Appendix F. Device Use Diary

Appendix G. PedEyeQ Questionnaire

Appendix H. PROMIS QoL Questionnaires

Appendix I. LVQOL Questionnaire

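### The Ability Questionnaire rule credits a child only when all 12 items are rated 3 or greater, so a device that more than doubles the rate on every item can still be judged not efficacious on this endpoint

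*Combined protocol and SAP*

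**What the plan says.** Section 9.4.3 defines the Ability Questionnaire analysis as "Proportions of participants with scores 3 or greater in all items from 1-12". Its rule for success requires a "25% increase in the proportion of participants scoring 3 or greater in all items", and either post-baseline visit, set against baseline, may supply it. The section adds: "No formal statistical tests will be conducted. Interpretation of results will be rule-based". It plans no total score, item count or paired change for this questionnaire. It gives no reason for requiring every item, and it does not say whether 25% is relative or in percentage points.

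Section 8.2.1 describes the instrument as parent-completed "questionnaires of their child's ability to accomplish the tasks in the Function Test without help". Section 4.1 sets the denominator: "The primary and secondary objectives will be assessed using data from all 30 participants". The other secondary endpoint, the Function Test score, is a "sum of items 1 to 7 combining levels a & b and will range from 0 to 14", and its rule counts the children whose own score rises by at least 30%.

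**The concern.** Requiring all 12 items turns 12 ratings per child into one yes or no. A child who improves on many tasks but stays below 3 on one contributes nothing, and a single task out of reach blocks that child at every visit. Section 3 expects neurocognitive disability in the CLN3 group, which is 20 of the 30 participants, so an out-of-reach item is a realistic prospect.

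Two things are at stake. This is one of two secondary efficacy endpoints, and its rule can return a negative conclusion when every task has improved. Section 9.2 also says that a major purpose of the pilot is to find outcome measures that appear to improve with device use and to inform the power calculation of a later trial. An all-or-nothing proportion hides much of that information.

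**Working it through.** The plan states no power or error rate for this rule, so there is no figure to reproduce. The simulations in section 9.4.3 concern a paired t-test on Function Test scores with N = 10 and do not bear on it.

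**Inputs from the documents.** 12 items; a child counts only if all 12 are at 3 or greater; N = 30; either post-baseline visit may meet the rule. In percentage points, 0.25 × 30 = 7.5, so a net gain of at least 8 children is needed.

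**Inputs assumed.** Item rates, and the correlation between items, are not in the documents. The range is shown below. All 30 children are taken as rated at every visit.

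**Step 1: a case that needs no assumed rates or correlations.** Every child goes from 5 to 11 items at 3 or greater.
- Average item rate: 5/12 = 42% before, 11/12 = 92% after, a ratio of 2.2.
- Spread as evenly as 30 children allow, each item has 12 or 13 children at baseline (150/12 = 12.5) and 27 or 28 afterwards (330/12 = 27.5). Even the least favourable pairing, 27/13 = 2.08, more than doubles.
- All-12 proportion: 0/30 before and 0/30 after. There is no increase on either scale, so the rule is not met.

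**Step 2: independent items, rate 30% to 70%.** The all-12 proportion goes from 0.3^12 = 0.0000005 to 0.7^12 = 0.0138, which is 30 × 0.0138 = 0.4 child expected. P(at least 8 of 30) = 6 × 10^-9.

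**Step 3: correlated items.** One-factor probit model with the same child factor at each visit:

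P(all 12) = ∫ Φ[(Φ⁻¹(p) + √ρ·z)/√(1−ρ)]^12 φ(z) dz.

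Item rate 30% to 70%, 25 percentage points, simulated:

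| ρ | All-12 proportion | Met at one given visit | Met at either visit |
|---|---|---|---|
| 0.3 | 0.3% to 12% | 2% | 4% |
| 0.5 | 1.8% to 22% | 25% | 38% |
| 0.7 | 5.6% to 34% | 65–66% | 78–79% |
| 0.9 | 14% to 50% | 91% | 95% |

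In every row the mean gain is 12 × (0.70 − 0.30) = 4.8 items per child.

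**Step 4: a larger effect.** For 40% to 90%, the rule is met at either visit in about 87% of trials at ρ = 0, and in 99.9% or more at ρ = 0.3 and above.

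**Step 5: the relative reading.** For 30% to 70%, the baseline is 0 of 30 in about 90%, 58% and 17–19% of trials at ρ = 0.3, 0.5 and 0.7, and a relative increase from zero is undefined. If any rise from zero counts, the rule is met in 99.8% of trials or more. With no effect (30% at all visits) it is still met in about 13%, 33% and 44%. With no effect at 50% and ρ = 0.5, it is met in 42.4% of trials from a non-zero baseline plus 8.2% from zero, about 51% in all.

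**Step 6: the item-by-item reading.** If each item's own proportion must rise, then for 30% to 70% all 12 do so at a given visit in 0.27–0.44 of trials for 25 percentage points, and in 0.91–0.97 for 25% relative (ρ from about 0 to 0.5).

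**The case against.** The strongest reply is that Step 1 proves only possibility. Strong correlation between items is plausible, because one parent rates one child on tasks that share one visual deficit. At ρ = 0.7 the rule is met in most trials even for 30% to 70%, and after a larger effect it is met nearly always. This stands. A reader might infer that the rule will usually fail a helpful device; the documents give neither item rates nor correlations, so they do not support that.

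A reader might also infer that the rule is too strict whichever percentage scale is meant. Step 5 shows otherwise: on a relative scale it tends to be undefined or too lenient. That is a different failure of the same definition.

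The plural in "Proportions of participants with scores 3 or greater in all items from 1-12" allows an item-by-item reading, under which no child is blocked by one item and item-level results would be reported. That reading is possible and milder, though less natural, and it still requires all 12 items to rise.

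The questionnaire's content cannot be used here. The available text carries only the title "Appendix D. Ability Questionnaire", so the meaning of a 3 and the top of the scale are unknown. It is tempting to treat 12 questionnaire items against 7 Function Test items as a mismatch. The Function Test has two levels per item and neither form is visible, so no such conclusion follows.

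Finally, this rule does not decide efficacy alone. The Function Test has its own within-child rule, and no stopping rule is tied to this endpoint.

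**Conclusion.** The concern holds as a defect of definition. On the natural reading of section 9.4.3, 11 of 12 items counts as 0 of 12, and the rule can give a negative result on this endpoint when the rate on every item has more than doubled. That much rests on the text and simple counting.

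The frequency is conditional. With 30 children, a percentage-point threshold, either visit and item rates of 30% to 70%, the chance of meeting the rule runs from about 4% to 79% as latent correlation goes from 0.3 to 0.7. With 40% to 90% it is 87% or more. The unstated scale of the 25% is a second gap, which on a relative reading can make the rule undefined, or met with no true effect in up to roughly half of trials in the settings examined.

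This should be fixed before data are seen. It is not critical, because the endpoint is secondary, rule-based and untested, in a pilot. The documents do not support reading it as a threat to the trial's overall efficacy conclusion, since the plan does not say how the two secondary rules combine.

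**What to change.** In section 9.4.3:

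1. Score each child at each visit as the number of the 12 items rated 3 or greater (0–12).
2. Report the mean paired change from baseline with a 95% CI at 1 week and at 1 month, together with the proportion at 3 or greater for each item.
3. Base the rule on within-child gain, in parallel with the Function Test rule. One example is at least 25% of all participants gaining 3 or more items (25% of 12) at 1 week or 1 month. Fix the threshold before data are seen.
4. Keep the all-12 proportion as a descriptive line, with its change in percentage points.

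The cost is wording; no new data are needed. The 3-item cut-off is a chosen value that the documents do not supply, so the sponsor should justify it. In the same model the example rule is met in essentially all trials for 30% to 70%. With no effect it is met in at most about 6% of trials when items are correlated, and in up to about 15% if items are independent at a 50% rate.
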